Appendix 1a Schedule of Activities (cont.)

[REDACTED]

[REDACTED]

[REDACTED]

^y Day 1 serum PK samples are to be drawn 30 (\pm 5) minutes pre-dose of MHAA4549A, 60 (\pm 15) minutes after the end of infusion. Serum PK samples on Day 2 and after are to be drawn immediately before oseltamivir dosing. PK samples will be drawn from the contralateral arm from that used for drug infusion and must be labeled with the exact time of draw.

[REDACTED]

^{aa} If patient is discharged on or before Day 5, the oseltamivir PK samples are to be taken on the discharge day.

[REDACTED]

[REDACTED]

^{dd} Patients who are discharged from the hospital with oseltamivir will be required to complete a medication diary and return the medication diary, empty (used) oseltamivir packets and unused oseltamivir capsules to the study site at the next follow up visit. Patients will record the date and time when each oseltamivir capsule is administered.

Appendix 1a

Schedule of Activities (cont.)

^{ee} Indicate which clinical status the patient is categorized under: death; in the ICU; non-ICU hospitalization, requiring supplemental oxygen; non-ICU hospitalization, not requiring supplemental oxygen; not hospitalized, but unable to resume normal activities; or not hospitalized with full resumption of normal activities

Appendix 1b Schedule of *Activities*: Follow-Up Period

- If a patient is discharged prior to Day 14, he/she will need to complete the following assessments for Day 14, Day 30, and Day 60 below.
- If a patient is discharged after Day 14 but prior to Day 30, he/she will need to complete the following assessments for Day 30 and Day 60 below.
- If a patient is discharged after Day 30, but prior to Day 60, he/she will need to complete the following assessments for Day 60 below.
- If patient is hospitalized for Day 14, Day 30, and/or Day 60, please refer to Appendix 1a.

Day (D)	D14 ± 1 (If discharged BEFORE Day 14)	D30 ± 4 (If discharged BEFORE Day 30)	Day 60 ± 7 (Study Completion) or Early Discontinuation
Concomitant medications ^a	x	x	x
Vital signs ^b	x	x	x
Electrocardiogram (12-lead) ^c	x	x	x
Weight, BMI ^d	x	x	x
Adverse events	x	x	x
Hematology ^e	x	x	x
Chemistry panel ^e	x	x	x
Coagulation panel ^e	x	x	x
Urinalysis ^e	x	x	x
Flu antibodies (HAI)	x	x	x
[REDACTED]		x	x
Serum for MHAA4549A PK measurements ^f	x	x	x
[REDACTED]	x	x	x
[REDACTED]	x	x	x
[REDACTED]		x	x
[REDACTED]		x	x
[REDACTED]		x	x

Appendix 1b Schedule of Activities: Follow-Up Period (cont.)

Day (D)	D14 ± 1 (If discharged BEFORE Day 14)	D30 ± 4 (If discharged BEFORE Day 30)	Day 60 ± 7 (Study Completion) or Early Discontinuation
[REDACTED]		x	x
Clinical status assessment^h	x	x	

[REDACTED]; ATA = Anti-therapeutic antibodies; BMI = body mass index; D = day;
 Dx = diagnostics; eCRF = electronic Case Report Form; ECG = electrocardiogram; HAI = hemagglutinin inhibition; [REDACTED]
 [REDACTED] PD = pharmacodynamics; PK = pharmacokinetic.

- ^a Concomitant medications should be recorded for 30 days prior to screening, through the study completion/early discontinuation visit. See exclusion criteria in [Section 4.1.2](#) for prohibited therapies.
- ^b Vital signs include temperature, respiratory rate, heart rate, systolic blood pressure, and diastolic blood pressure. Temperature should be measured using the same methodology throughout the study and should be measured prior to study drug administration of any antipyretic drugs. In patients who have multiple vital signs taken during any day, the most abnormal value should be recorded from that 24-hour period. Temperature, blood pressure, respiratory rate, and heart rate will be completed after the patient has been in a seated or supine position for > 5 minutes.
- ^c ECG should be recorded after the patient has rested in a supine position for 10 minutes.
- ^d Weight will be recorded in kg.
- ^e Local laboratory measurements should be used.
- ^f PK samples must be labeled with the exact time of draw.

^h Indicate which clinical status the patient is categorized under: death; in the ICU; non-ICU hospitalization, requiring supplemental oxygen; non-ICU hospitalization, not requiring supplemental oxygen; not hospitalized, but unable to resume normal activities; or not hospitalized with full resumption of normal activities

Appendix 2

Time to Normalization of Respiratory Function

For the purposes of this study, the time to normalization of respiratory function will be defined as the time to removal of the patient from O₂ supplementation in order to maintain an SpO₂ ≥95%.

*Unless clinically contraindicated**, patients who are on low flow O₂ (i.e., 2-6 L/min) should receive a daily trial off O₂ in the morning between 6:00 a.m. and 12:00 noon as described below.

1. Patient should be resting or sitting.
2. Patient should be fitted with pulse oximeter, and their SpO₂ should be checked once while on O₂ and then again 3 – 5 minutes after turning off O₂ supplementation. *Clinical judgment should be used to determine when the SpO₂ result is stable to record.*
3. If the SpO₂ ≥95%, then the time and reading should be recorded. Notify the study doctor so that he/she can make a clinical judgment to determine whether the O₂ can be removed.
4. The recorded time for the endpoint corresponds with the initial discontinuation of O₂ and reading.

If a patient is clinically able to be removed from oxygen outside the time window above (6:00 a.m. and 12:00 noon), the trial off data should be recorded as an unscheduled visit.

** If a patient has an SpO₂ <95% while on oxygen supplementation, he/she shall be considered to be “clinically contraindicated” from requiring a trial off oxygen; however, corresponding respiratory assessments should be recorded.*

Appendix 3

[Redacted]

[Redacted]

[Redacted]

[Redacted]

[Redacted]

Appendix 4

[Redacted]

[Redacted]

[Redacted]

[Redacted]

[Redacted]

Appendix 5

[Redacted]

[Redacted]

[Redacted]

[Redacted]

[Redacted]

[Redacted]

[Redacted]

[Redacted]

[Redacted]

[Redacted]

[Redacted]

[Redacted]

[Redacted]

[Redacted]

[Redacted]

Appendix 6

[REDACTED]

[REDACTED]

[REDACTED]

[REDACTED]

[REDACTED]

[REDACTED]

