3.3.2 Primary Efficacy Outcome Measures

The primary efficacy outcome measure for this study *is* as follows:

- Time to normalization of respiratory function defined as:
 - The time to cessation of O₂ support resulting in a stable SpO₂ ≥ 95% (see [Appendix 2](#) for details)

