6.1 DETERMINATION OF SAMPLE SIZE

The purpose of this study is estimation of the effect size and hypothesis generation regarding the effect of MHAA4549A on the time to normalization of respiratory function relative to the standard of care rather than hypothesis testing. Point and interval estimates will be obtained. Approximately 330 patients will be enrolled. It is assumed that the median time to normalization of respiratory function in the control arm is 5 days. This sample size (approximately 110 patients per arm) provides 71% power to detect a

treatment difference of 1 day for the primary endpoint in both MHAA4549A arms assuming a 2-sided alpha of 0.2 and no difference in efficacy between the two active arms. If the 3600-mg dose shows a treatment difference of 1 day and the 8400-mg dose shows a treatment difference of 1.5 days or more then this sample size provides > 86% power assuming a 2-sided alpha of 0.2.

Operating characteristics (power) under other possible assumptions for 2-sided alpha of 0.2 and true differences of 0.5 to 2 days are provided in [Table 7](#).

Table 7 Operating Characteristics for Proposed Study Design for Several Possible True Underlying Median Values

	True Underlying Median for MHAA4549A							
	3600	8400	3600	8400	3600	8400	3600	8400
	mg	mg	mg	mg	mg	mg	mg	mg
	4 days	4 days	4 days	3.5 days	4 days	3 days	4.5 days	4 days
Hazard Ratio	0.8	0.8	0.8	0.7	0.8	0.6	0.9	0.8
Power of log-rank test ^a	71.4%		86.6%		98.8%		56.2%	

Note: Operating characteristics are based on the following assumptions: 330 evaluable patients, event times are exponentially distributed, median time to normalization of respiratory function in the control arm is 5 days, and patients are followed for 60 days.

^a Two-sided $\alpha = 0.20$.

It should be noted that the study is underpowered for detection of minimally clinically meaningful differences at a 2-sided alpha of 0.05 such as a true hazard ratio of 0.80 in both MHAA4549A arms.

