Appendix 1a Schedule of *Activities*

Notes: Unless otherwise indicated, **all assessments on Day 1 should be performed prior to study drug administration**; x's within parentheses, i.e., (x), indicate optional assessments. Please refer to Follow-up Period table for visits to be completed after patient is discharged from hospital prior to Day 60. Any screening assessments completed prior to consent as standard of care do not need to be repeated if done within the screening period. If a patient is unable to be present at the site for a follow-up visit, a telephone visit is *encouraged*.

Hospitalized Days (only to be completed while patients are hospitalized)																						
	D -2,-1	D1 (Randomization)	D2	D3	D4	D5	D6	D7	D8	D9	D10	D11-13	D14	D15-19	D20	D21-24	D25	D26-29	D30	Hospital Discharge ^a	D60 Study Completion or Early Discontinuation while hospitalized	Unscheduled
Informed consent ^b	x																					
Sponsor-approved influenza test ^c	x																					
Inclusion/exclusion criteria	x																					
Medical history and demographic	x																					

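### Oxygen use and SpO2 are not collected after discharge, so the primary endpoint cannot be scored for patients who go home event-free, and no analysis rule covers them

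*Combined protocol and SAP*

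**What the plan says.** All references are to protocol Version 7.

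- **Endpoint.** Section 3.3.2 defines it as the time to cessation of oxygen "support resulting in a stable" SpO2 of at least 95%. It is found through a daily trial off oxygen (Section 4.6.9, Appendix 2).
- **In hospital.** The Respiratory Assessment row is in Appendix 1a, whose columns are "only to be completed while patients are hospitalized". For a patient who leaves, the Hospital Discharge column is the last reading.
- **After discharge.** The visible rows of Appendix 1b (Days 14, 30, 60) contain no respiratory assessment. Footnote b says: "Vital signs include temperature, respiratory rate, heart rate, systolic blood pressure, and diastolic blood pressure". Section 4.6.8 gives the same list, yet Section 6.5 counts SpO2 among the vital signs to be analysed.
- **Analysis.** Section 6.4 censors patients lost to follow-up while event-free at the last time they were known to be so, and allows no other imputation.
- **Planning.** "It is assumed that the median time to normalization of respiratory function in the control arm is 5 days" (Section 6.1). "This sample size (approximately 110 patients per arm) provides 71% power to detect a" difference of 1 day in both active arms, "assuming a 2-sided alpha of 0.2 and no difference in efficacy between the two active arms". The note to Table 7 adds 330 evaluable patients, exponential times, and that "patients are followed for 60 days".

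**The concern.** Entry turns on an SpO2 of 92%, the event on 95% off oxygen, and no passage ties discharge to the event. A patient on room air at 93% or 94%, or one sent home with oxygen, leaves without having met the endpoint. That patient is not lost, because the Day 14, 30 and 60 visits still take place, but nothing scheduled there can show when or whether the endpoint was reached. The clinical status scale at Days 14 and 30 does not help, since its two categories for discharged patients do not record oxygen use.

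If the only stated rule is extended to these patients, their follow-up for the primary endpoint ends at discharge. Doctors discharge patients partly on respiratory grounds, so that censoring is unlikely to be independent of the time still needed to recover. Section 6.1 gives effect estimation as the purpose of the study, so what is at stake is the estimate itself as well as the number of events.

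**Working it through.** **1. The plan's own figure.** Inputs from Section 6.1 and Table 7: medians 5, 4 and 4 days, 330 evaluable patients, two-sided alpha 0.20, 60 days. Table 7 writes the hazard ratio as 0.8; as an event-rate ratio for active against control it is 5/4 = 1.25.

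- Expected events by day T: 110 × [(1 − 2^(−T/5)) + 2 × (1 − 2^(−T/4))]. At T = 60 this is 330.
- Freedman's formula, pooled active against control (k = 2, h = 1.25): power = Φ(√(D·k)·|1 − h|/(1 + k·h) − 1.2816). With D = 330: √660 × 0.25/3.5 − 1.2816 = 1.835 − 1.282 = 0.553, so 71.0%. A simulated log-rank test gives 72.0%. The stated 71.4% is reproduced, on the basis that practically every patient has an observed event.
- The 60-day horizon by itself matters little. T = 30 gives 327 events and 70.7%; T = 14 gives 295 events and 67.5%.

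**2. Events lost.** The share discharged event-free (q) is not in the documents, so it is assumed to be 10%, 20% or 30%. In the scenario used, recovery times are exponential with median 5 days, and affected patients leave an exponential time (mean 3 days) before they would have recovered, but not before day 0.5. The 6.7% who recover before day 0.5 (1 − 2^(−0.1)) still count as events.

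Events = 330 × (1 − q × 2^(−0.1)); power is Freedman's formula on those events.

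| q | Events | Power if the loss is unrelated to recovery |
|---|---|---|
| 0 | 330 | 71.0% |
| 10% | 299 | 67.9% |
| 20% | 268 | 64.5% |
| 30% | 238 (237 to 238 between runs) | 60.9% |

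**3. Direction for the medians.** A second simulation puts the discharge decision at days 2 to 9 (assumed), with the same policy in all arms and about 24% of control and 20% of active patients leaving event-free. The control Kaplan-Meier median is 5.6 days if those close to recovery leave, 4.7 days if slow recoverers leave, and 5.0 days if discharge is unrelated to recovery.

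**4. Effect on the comparison (true event-rate ratio 1.25).**

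| Who leaves event-free | Control / active share | Estimated ratio |
|---|---|---|
| Unrelated to recovery | 24% / 20% | 1.24 |
| Near recovery, same policy | 24% / 20% | 1.30 |
| Slow recoverers, same policy | 24% / 20% | 1.25 |
| Near recovery, shares differ | 5% / 16% | 1.13 |
| Slow recoverers, shares differ | 5% / 16% | 1.47 |

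Under the scenario of step 2, equal shares of 10% to 30% give ratios between 1.25 and 1.28. Shares of 5% and 20% give 1.12 to 1.13. With no true effect and shares of 5% and 19% (second simulation), the chance of a result favouring the drug is 1% if near-recovered patients leave and 57% if slow recoverers leave, against a nominal 10%.

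**The case against.** **The censoring is inferred.** Section 6.4 speaks only of loss to follow-up, and Section 6 defers further detail to a separate SAP. This is right: the plan does not say that these patients are censored at discharge. But a SAP can choose a rule; it cannot supply readings that were never taken. Concomitant medication records to Day 60 might show when oxygen stopped, but not the SpO2.

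**Redaction.** Some rows of Appendix 1b are blacked out. The Respiratory Assessment row is legible in Appendix 1a, so it is unlikely to be one of them.

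**Few patients may be affected.** Patients on home or baseline oxygen, and those with chronic lung disease and a documented SpO2 below 95% off oxygen, are excluded. Discharge readings and unscheduled trials off oxygen are recorded, so only normalization after discharge is missed. This limits the size, and no share can be taken from the documents.

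**The comparison is protected.** The trial is double-blind, so discharge shares should differ by arm only through the treatment's own effect or by chance. With equal shares the ratio hardly moves. This stands, and it is why the point is a cheap improvement and not a fatal flaw. A stratified Cox model also absorbs much of any difference in discharge practice between countries, if country is among its strata.

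**Power carries little weight.** Section 6 disclaims formal testing, and the power losses in the working assume that the hazard ratio is intact. Agreed.

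**Conclusion.** The gap is real: the components of the primary endpoint are not collected after discharge, event-free discharge is possible, and no rule covers it. An assumed 10% to 30% of patients leaving event-free would cost roughly 31 to 92 of 330 events. The hazard ratio is little affected when shares are equal. It can be materially distorted when they differ, for example about 1.13 instead of 1.25 with 5% against 20% sent home near recovery. All these sizes rest on assumed shares and discharge patterns.

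Three stronger readings are tempting and not supported:

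- That medians are biased upward. They rise if near-recovered patients leave and may fall if slow recoverers leave; the documents do not say which.
- That a shift in one arm's median can be set against the 1-day planning difference. A shift shared by the arms is not a shift in their difference.
- That the 60-day assumption in Table 7 is itself the error. A 30-day horizon gives nearly the same power; what matters is the assumption that nearly every event is observed.

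Separately, Section 3.3.2 asks for a stable reading, while Appendix 2 says: "The recorded time for the endpoint corresponds with the initial discontinuation of" oxygen. The two passages should be reconciled; no more than that follows from the text.

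**What to change.** - **Appendix 1b, Days 14, 30 and 60:** add room-air SpO2, current oxygen use and the date oxygen stopped. Ask the oxygen questions by telephone where there is no visit; the notes to Appendix 1a already encourage such calls. Bring footnote b and Section 4.6.8 into line with Section 6.5.
- **Section 6.4:** state that patients discharged event-free are not censored at discharge. Analyse them with interval-censored timing, from discharge to the first contact showing normalization.
- **Sensitivity analyses:** count these patients as having the event at discharge, and separately as event-free to Day 60.
- **Reporting:** give the share discharged event-free by arm, so that readers can see whether it differs.

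The cost is one oximeter reading, two short questions and an added eCRF item at visits that already exist, plus analysis wording. The drawback is coarse timing after discharge, and a telephone contact gives oxygen use but no SpO2.

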Appendix 7 SOFA Score Calculation

Variables	SOFA Score				
	0	1	2	3	4
Respiratory (PaO ₂ /FiO ₂ , mmHg)	> 400	≤ 400	≤ 300	≤ 200 ^a	≤ 100 ^a
Coagulation (Platelets x 10 ³ /μL) ^b	> 150	≤ 150	≤ 100	≤ 50	≤ 20
Liver (Bilirubin, mg/dL) ^b	< 1.2	1.2–1.9	2.0–5.9	6.0–11.9	> 12.0
Cardiovascular (Hypotension)	No hypotension	MAP < 70 mmHg	Dop ≤ 5 or dob (any dose) ^c	Dop > 5, epi ≤ 0.1, or norepi ≤ 0.1 ^c	Dop > 15, epi > 0.1, or norepi > 0.1 ^c
Central Nervous System (Glasgow Coma Score Scale)	15	13–14	10–12	6–9	< 6
Renal (Creatinine, mg/dL or urine output, mL/day) ^d	< 1.2	1.2–1.9	2.0–3.4	3.5–4.9 or < 500	> 5.0 or < 200

Norepi = norepinephrine; Dob = dobutamine; Dop = dopamine; Epi = epinephrine; FiO₂ = fraction of inspired oxygen; MAP = mean arterial pressure; PaO₂ = partial pressure of arterial oxygen.

^a Values are with respiratory support.

^b To convert bilirubin from mg/dL to μmol/L, multiply by 17.1.

^c Adrenergic agents administered for at least 1 hour (doses given are in μg/kg per minute).

^d To convert creatinine from mg/dL to μmol/L, multiply by 88.4.

References for Appendix 7:

Vincent JL, de Mendonca A, Cantraine F et al. Use of the SOFA score to assess the incidence of organ dysfunction/failure in intensive care units: results of a multicenter, prospective study. Working group on “sepsis-related problems” of the European Society of Intensive Care Medicine. *Crit Care Med* 1998;26(11): 1793–1800.

Appendix 8
DAIDS Toxicity Grading Tables for Clinical Abnormalities

From the FDA Guidance document ‘Toxicity Grading Scale for Healthy Adult and Adolescent Volunteers Enrolled in Preventative Vaccine Clinical Trials’ (September 2007)

Vital Signs ^a	Mild (Grade 1)	Moderate (Grade 2)	Severe (Grade 3)	Potentially Life Threatening (Grade 4)
Fever (°C) ^b (°F)*	38.0 – 38.4 100.4 – 101.1	38.5 – 38.9 101.2 – 102.0	39.0 – 40.0 102.1 – 104.0	>40 >104
Tachycardia – beats per minute	101- 115	116 – 130	>130	ER visit or hospitalization for arrhythmia
Bradycardia – beats per minute ^c	50 – 54	45 – 49	<45	ER visit or hospitalization for arrhythmia
Hypertension (systolic) – mmHg	141 – 150	151 – 155	>155	ER visit or hospitalization for malignant hypertension
Hypertension (diastolic) – mmHg	91 – 95	96 – 100	>100	ER visit or hospitalization for malignant hypertension
Hypotension (systolic) – mmHg	85 – 89	80 – 84	<80	ER visit or hospitalization for hypotensive shock
Respiratory Rate – breaths per minute	17 – 20	21 – 25	>25	Intubation

^a Subject should be at rest for all vital sign measurements.

^b Oral/tympanic temperature; no recent hot or cold beverages or smoking.

^c When resting heart rate is between 60 – 100 beats per minute. Use clinical judgment when characterizing bradycardia among some healthy subject populations, for example, conditioned athletes.

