5.2.2 Serious Adverse Events (Immediately Reportable to the Sponsor)

A serious adverse event is any adverse event that meets any of the following criteria:

- Fatal (i.e., the adverse event actually causes or leads to death)
- Life threatening (i.e., the adverse event, in the view of the investigator, places the patient at immediate risk of death)

This does not include any adverse event that had it occurred in a more severe form or was allowed to continue might have caused death.

- Requires or prolongs inpatient hospitalization (see [Section 5.3.5.10](#))
- Results in persistent or significant disability/incapacity (i.e., the adverse event results in substantial disruption of the patient's ability to conduct normal life functions)
- Congenital anomaly/birth defect in a neonate/infant born to a mother exposed to study drug

- Significant medical event in the investigator's judgment (e.g., may jeopardize the patient or may require medical/surgical intervention to prevent one of the outcomes listed above)

The terms "severe" and "serious" are not synonymous. Severity refers to the intensity of an adverse event (e.g., rated as mild, moderate, or severe, or according to Division of AIDS Table for Grading the Severity of Adult and Pediatric Adverse Events [DAIDS]; see [Section 5.3.3](#), [Appendix 8](#), and [Appendix 9](#)); the event itself may be of relatively minor medical significance (such as severe headache without any further findings).

Severity and seriousness need to be independently assessed for each adverse event recorded on the eCRF.

Serious adverse events are required to be reported by the investigator to the Sponsor immediately (i.e., no more than 24 hours after learning of the event; see [Section 5.4.2](#) for reporting instructions).

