5.3.3 Assessment of Severity of Adverse Events

Investigators will seek information on adverse events and serious adverse events at each patient contact. All adverse events, and serious adverse events, whether reported by the patient or noted by authorized study personnel, will be recorded.

The adverse event grading (severity) scale in the DAIDS v1.0 will be used for assessing adverse event severity (see [Table 5](#)).

Table 5 Adverse Event Grading (Severity) Scale

PARAMETER	GRADE 1 MILD	GRADE 2 MODERATE	GRADE 3 SEVERE	GRADE 4 POTENTIALLY LIFE- THREATENING
ESTIMATING SEVERITY GRADE				
Clinical AE NOT identified elsewhere in this DAIDS AE Grading Table	Symptoms causing no or minimal interference with usual social and functional activities	Symptoms causing greater than minimal interference with usual social & functional activities	Symptoms causing inability to perform usual social & functional activities	Symptoms causing inability to perform basic self-care functions OR Medical or operative intervention indicated to prevent permanent impairment, persistent disability, or death

AE = adverse event; DAIDS = Division of Acquired Immunodeficiency Syndrome.

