6.5 SAFETY ANALYSES

The safety analyses will include all randomized patients who received study drug, with patients grouped according to the treatment actually received. Safety parameters to be evaluated include AEs (including deaths, SAEs, discontinuations due to AEs, and the incidence and severity of AEs), clinical laboratory tests, vital signs (including SpO₂ measurements), and ECGs.

All collected AE event data will be listed by study site and patient number. All AEs that occur on or after treatment on Day 1 will be summarized for each treatment group by mapped term, appropriate thesaurus levels, body system, and event within each body system, and toxicity grade. In addition, all SAEs, including deaths, will be listed separately and summarized. SAEs caused by a protocol mandated intervention (e.g., invasive procedures such as biopsies, discontinuation of medications) that occur between consent and first dose of study medication will be listed separately.

Laboratory data with values outside of the normal ranges will be identified. In addition, select laboratory data will be summarized by treatment group using descriptive summary statistics.

The absolute and percentage changes from baseline in vital sign parameters will be computed, and changes deemed clinically significant by the Investigator will be noted. Appropriate descriptive summary statistics will be provided for all vital sign parameters

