Appendix 8 (cont'd)
DAIDS Toxicity Grading Tables for Clinical Abnormalities

Systemic (General)	Mild (Grade 1)	Moderate (Grade 2)	Severe (Grade 3)	Potentially Life Threatening (Grade 4)
Nausea/vomiting	No interference with activity or 1–2 episodes/ 24 hours	Some interference with activity or >2 episodes/ 24 hours	Prevents daily activity, requires outpatient IV hydration	ER visit or hospitalization for hypotensive shock
Diarrhea	2–3 loose stools or <400 g/ 24 hours	4–5 stools or 400–800 g/ 24 hours	5 or more watery stools or >800 g/ 24 hours or requires outpatient IV hydration	ER visit or hospitalization
Headache	No interference with activity	Repeated use of non-narcotic pain reliever >24 hours or some interference with activity	Significant; any use of narcotic pain reliever or prevents daily activity	ER visit or hospitalization
Fatigue	No interference with activity	Some interference with activity	Significant; prevents daily activity	ER visit or hospitalization
Myalgia	No interference with activity	Some interference with activity	Significant; prevents daily activity	ER visit or hospitalization

Systemic Illness	Mild (Grade 1)	Moderate (Grade 2)	Severe (Grade 3)	Potentially Life Threatening (Grade 4)
Illness or clinical adverse event (as defined according to applicable regulations)	No interference with activity	Some interference with activity no requiring medical intervention	Prevents daily activity and requires medical intervention	ER visit or hospitalization

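### Section 5.3.3 grades adverse events by DAIDS v1.0, but the appendix labelled DAIDS is a healthy-volunteer vaccine scale with a rival catch-all row and criteria that do not separate grades in inpatients

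*Combined protocol and SAP*

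**What the plan says.** All references are to protocol Version 7. Section 5.3.3 states: "The adverse event grading (severity) scale in the DAIDS v1.0 will be used for assessing adverse event severity". It points to Table 5, whose single row is labelled "Clinical AE NOT identified elsewhere in this DAIDS AE Grading Table". Grade 4 there begins with "Symptoms causing inability to perform basic self-care functions"; the alternative is intervention needed to avert lasting harm or death. Hospitalization plays no part.

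Section 5.2.2 names the Division of AIDS table as a way of rating severity and refers the reader to Section 5.3.3, Appendix 8 and Appendix 9. It also says that seriousness and severity are to be judged independently, and it lists hospitalization, or its prolongation, as a seriousness criterion.

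Appendix 8 is headed "DAIDS Toxicity Grading Tables for Clinical Abnormalities", but the source printed beneath is the FDA document "Toxicity Grading Scale for Healthy Adult and Adolescent Volunteers Enrolled in Preventative Vaccine Clinical Trials". For several symptoms, and for a final row covering any illness or clinical adverse event, Grade 4 is "ER visit or hospitalization".

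Severity is part of the safety objective (Section 2.1). Section 6.5 summarizes adverse events for each treatment group by mapped term, body system, "and event within each body system, and toxicity grade".

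**The concern.** A site that follows the protocol meets two different scales under one name. One is functional and can be applied at the bedside. The other was written for healthy people living at home, for whom an emergency visit or an admission marks a bad outcome. In this trial everyone is already admitted.

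At stake is the upper end of the severity tables. If sites differ in the table they use, or in how they read the hospitalization criterion, Grade 3 and Grade 4 counts mix two measures. The scale can also affect the number of events: under Section 5.3.5.3, a persistent event that becomes more severe is entered as a new one.

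**Working it through.** The plan states no figure on this point, so the check compares the texts and counts rows.

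**1. Does Table 5 settle which scale governs?** No. By its own label it covers only events without a row elsewhere in the grading table. Listed events such as headache or diarrhea therefore go to a listing, and the clinical listing that the protocol supplies under the DAIDS name is Appendix 8. For unlisted events there are two generic rows:

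| | Table 5 | Appendix 8, last row |
|---|---|---|
| Applies to | clinical events not listed elsewhere | any illness or clinical adverse event |
| Grade 2 | more than minimal interference | some interference, and no medical intervention |
| Grade 3 | usual activities impossible | daily activity prevented, and intervention required |
| Grade 4 | self-care lost, or intervention to avert lasting harm or death | "ER visit or hospitalization" |

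Take an event that causes some interference and is treated with a drug. Table 5 makes it Grade 2. In the Appendix 8 row it fails Grade 2 because it was treated, and fails Grade 3 because activity was not prevented.

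**2. How many Appendix 8 rows depend on hospitalization?** There are 7 vital-sign rows + 5 systemic rows + 1 catch-all = 13.

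- Grade 4 mentions an emergency visit or hospitalization in 11 of the 13. Fever (a temperature) and respiratory rate (intubation) are the other two.
- In 6 of the 11 the visit or admission must be for a named condition: tachycardia and bradycardia (arrhythmia), systolic and diastolic hypertension (malignant hypertension), hypotension and nausea/vomiting (hypotensive shock).
- In 11 − 6 = 5 no cause is stated: diarrhea, headache, fatigue, myalgia and the catch-all.

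**3. Can those 5 rows separate grades in an inpatient?** Sections 4.1 and 4.1.1 plan about 330 patients, all hospitalized at entry. Read literally, every such event during the index stay meets Grade 4. Read causally, so that the event itself must bring about the visit or admission, a patient already in a bed cannot meet it, unless prolonged stay is counted. Prolonged stay is the seriousness criterion of Section 5.2.2. None of these readings orders inpatients by severity.

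**4. Grade 3.** Nausea/vomiting at Grade 3 includes a need for intravenous hydration as an outpatient, and for diarrhea this is one of three routes. It cannot occur during the index stay.

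**The case against.** The strongest reply is that Section 5.3.3 is the operative text and refers only to Table 5, while the reference to Appendix 8 in Section 5.2.2 sits inside an example explaining severe versus serious. This limits the problem but does not remove it: Table 5 excludes listed events, and the appendix carries the DAIDS name.

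Several further points stand and bound the size. Six of the 11 hospitalization rows need a named cause, so an influenza admission does not trigger them. The natural reading of the other five is causal, so the protocol does not itself say that any mild inpatient event is Grade 4. Events are collected to Day 60, and after discharge the criterion does discriminate. Deaths and serious events are summarized separately from grade.

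A reader might infer that the scale hides a difference between arms. Allocation is randomized, stratified by country and ventilation status, and blinded at the sites (Section 4.2), so the ambiguity should fall on the arms alike. Noise or dilution is the supportable claim.

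A reader might also infer that the intubation and respiratory-rate row fills the tables with disease. Section 5.3.5.9 keeps anticipated influenza deterioration out of the adverse events unless it is unexpected, Section 5.3.5.5 does not make every abnormal vital sign an event, and positive pressure ventilation includes a mask (Section 3.2.2). An unexpected intubation would plausibly be Grade 4 under Table 5 as well.

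Nor do the documents support discarding Appendix 9. Its laboratory rows are mostly numeric thresholds usable in inpatients, and the FDA footnote to the enzyme table attaches to one asterisked row (CPK). The Version 5 copy also cited a DMID table. The opening page of the Version 7 copy is not in the text available, so its source is a point to confirm.

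**Conclusion.** The grading source contradicts itself and should be reconciled. The defect comprises one mislabelled appendix, two competing catch-all rows, 5 of 13 rows whose Grade 4 does not separate inpatients, and 2 rows with a Grade 3 criterion that cannot arise during the index stay. The consequence is that Grade 3 and Grade 4 counts can be inconsistent across sites and may dilute a difference between arms. They also mix seriousness into severity, against Section 5.2.2.

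A reader might go further and call severity uninterpretable. The documents do not support that: Table 5 is usable, most laboratory thresholds are numeric, and the cause-specific rows can still be applied.

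The conclusion assumes that at least some sites grade from Appendix 8, which the documents permit but do not show. The number of events affected cannot be estimated, because no adverse event rates are given for this population. Beyond Table 5, the content of DAIDS v1.0 is not reproduced and was not checked.

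**What to change.** Make one scale govern in Sections 5.2.2 and 5.3.3, Table 5 and Appendix 8: DAIDS v1.0, which Section 5.3.3 already names. Keep Table 5 as the only catch-all row and delete the one in Appendix 8. For events during the index stay, remove the five unqualified hospitalization criteria and the outpatient-hydration criteria; the DAIDS v1.0 row, or Table 5 where none exists, then supplies the grade.

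Correct the source label of Appendix 8. Confirm that of Appendix 9 and keep its numeric laboratory thresholds. Before database lock, and while still blinded, check any events graded by the removed criteria. A rule counting only worsening from baseline is not needed, since Section 5.3.5.8 already records pre-existing conditions only if they worsen.

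The cost is an appendix edit, a memo to sites and a limited blinded check of grades.
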